1.1.4.2 Study RG012-05

A Phase 1 study evaluated the safety, tolerability, and PK of multiple SC doses of lademirsen (SAR339375) in healthy adult subjects (males and females between 18 and 55 years of age). In the double-blind, multiple ascending dose study, 8 subjects in each of 3 sequential dose cohorts were randomized in a 3:1 ratio to receive 5 once-weekly fixed doses of either lademirsen (SAR339375) or matching placebo, with lademirsen (SAR339375) dose escalation from 55 mg (Cohort 1) to 110 mg (Cohort 2) to 220 mg (Cohort 3) dependent on review of the safety and PK data in each cohort by a Safety Evaluation Committee (SEC). The SEC had approved escalation to the weekly 110 mg fixed dose (corresponding to approximately 1.5 mg/kg in a 73 kg subject) and to the weekly 220 mg fixed dose (corresponding to approximately 3.0 mg/kg in a 73 kg subject). A single AE of asymptomatic thrombocytopenia with a platelet count nadir of 92 000/microL that resolved spontaneously over 10 weeks was observed in the 220 mg cohort. The remaining 5 subjects in the 220 mg cohort also experienced a mild reduction in platelet count; however, these did not drop below the lower limit of normal (LLN) and resolved following discontinuation of study drug.

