7.1.2 Safety endpoints

- Incidence and severity of treatment-emergent AEs and serious adverse events (SAEs)
- Observed values and changes from baseline in clinical laboratory parameters (eg, hematology, chemistry, complement, and urinalysis)
- Observed values and changes from baseline in vital signs
- Observed changes from baseline in 12-lead ECG
- Observed changes from baseline in physical examinations
- Incidence and titer of ADAs
- Association of AEs with ADAs

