7.2.4 Safety analysis

The summary of safety results will be presented by treatment group. All safety analyses will be performed on the Safety Population. The baseline value is defined generally as the last available value before randomization. The treatment-emergent adverse event (TEAE) period is defined as the time between the first administration of study medication to the last administration of study medication plus 10 weeks follow up.

Adverse events will be presented by System Organ Class (SOC) and Preferred Term (PT) for each treatment group, the number (n) and percentage (%) of subjects experiencing an AE. The numbers and percentages of subjects with at least one TEAE, treatment-emergent SAE, TEAE leading to death, and TEAE leading to permanent treatment discontinuation will be tabulated by treatment group. In addition, TEAEs will be described according to maximum intensity and relation to the study drug.

- The following deaths summaries will be generated
Death in nonrandomized subjects or randomized and not treated subjects
- Treatment-emergent AE leading to death (death as an outcome on the AE eCRF page as reported by the Investigator) by primary SOC, HLG, HLT, and PT showing number (%) of subjects sorted by internationally agreed order of SOC and alphabetic order of HLG, HLT, and PT
- ACSI will be summarized by treatment group

Results and change from baseline for the laboratory parameters will be summarized by treatment group for baseline and each post baseline time point, endpoint, minimum and maximum value. Summary statistics will include number of subjects, mean, standard deviation, median, Q1, Q3, minimum, and maximum.

The following definitions will be applied to laboratory parameters.

- The potentially clinically significant abnormality (PCSA) values are defined as abnormal values considered medically important by the Sponsor according to predefined criteria/thresholds based on literature review and defined by the Sponsor for clinical laboratory tests.

- PCSA criteria will determine which subjects had at least 1 PCSA during the on-treatment period, taking into account all evaluations performed during the on-treatment period, including unscheduled or repeated evaluations. The number of all such subjects will be the numerator for the on-treatment PCSA percentage.

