4.7.3 Laboratory variables, vital signs and electrocardiograms (ECGs)

The summary statistics (including number, mean, median, Q1, Q3, standard deviation, minimum and maximum) of all laboratory variables (central laboratory values and changes from baseline) based on availability will be calculated for each visit or study assessments (baseline, each post-baseline time point, last on-treatment during placebo-controlled treatment period and lademirsen treatment period respectively, and worst on-treatment value during placebo-controlled treatment period and lademirsen treatment period respectively) by treatment group during the overall study period.

For selected laboratory parameters (eg, platelet, creatinine, proteinuria [protein/creatinine ratio], albumin/creatinine ratio, eGFR, and selected parameters in liver function), individual participant plots will be prepared for the observed value overtime during overall study period. For selected kidney parameters (eg, cystatin C, and blood urea nitrogen), mean (+/-SE) plots will be prepared for the observed value over time during the double-blind period, and also by screening eGFR stratification factor.

The incidence of PCSAs at any time during the placebo-control treatment-emergent period and lademirsen treatment-emergent period, respectively, will be summarized by biological function and treatment group whatever the baseline level is.

For PCSA analyses, the laboratory measurements obtained at either scheduled or unscheduled visits should be used; and, both the centralized and local test results should be used, as long as their available dates/time is different from each other's. Centralized data will be used

preferentially to the local measures in the PCSA analyses when measurements are performed on the same date and at the same time for a given laboratory test.

Listing of PCSAs during the overall study period will be provided.

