3 DESCRIPTION OF CHANGES

This SAP Version 2.0 addendum is developed prior to the final DBL (planned for 04 Nov 2022) by following decision to not start Stage 2 enrollment and study termination based on futility analysis result. As the study was terminated early, prior to all Stage 1 participants' completion of the double blind (DB) period of the study, and no Stage 2 participants are enrolled, only key endpoints are planned to be analyzed and the time frame of analysis is reduced to Week 48 for efficacy and most of the safety analyses. Only for limited key safety analyses, the analyses will include up to 96 weeks of the lademirsen treated period. No multiplicity adjustment will be performed. The modified objectives and endpoints are specified in Table 1, which is aligned with the endpoints defined in Amended Protocols 11, 12 and 13. However, there is no major change of the analysis plan regarding the statistical method. For efficacy analyses, as no Stage 2 participants are enrolled, all statistical method will only include Stage 1 participants, and the covariates only pertinent to Stage 2 participants will be removed.

Table 1 - Objectives and endpoints for final analysis (modified after the decision of study termination)

Population ^a	Objectives	Endpoints
Primary		
Primary population	To assess the efficacy of lademirsen in reducing the rate of decline in kidney function as compared to placebo in participants at risk for rapidly progressive Alport syndrome	Annualized rate of change in estimated glomerular filtration rate (eGFR) during the placebo-controlled treatment period
Secondary		
ITT population	To assess the efficacy of lademirsen in reducing the absolute decline in kidney function at Week 48	Absolute and percentage change in eGFR values from baseline at Week 24 and 48 Proportion of participants with a reduction from baseline in eGFR of <10%, <20%, <30%, or <40% at Week 24 and 48
ITT population	To assess the efficacy of lademirsen in delaying time to reach the ESRD	Number and proportion of participants who reach ESRD as defined by an eGFR ≤ 15 mL/min/1.73 m ² or initiation of hemodialysis or renal transplantation (composite endpoint) during the placebo-controlled treatment period

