Safety population for analysis during the placebo-controlled period; Lademirsen population for analysis during the lademirsen treatment period	To assess the safety and tolerability of lademirsen in participants with Alport syndrome. ^c	Incidence and severity of treatment-emergent adverse events (TEAEs) and serious adverse events (SAEs) during the placebo-controlled treatment period and lademirsen treatment period, respectively Number of participants with PCSA in clinical laboratory parameters during the placebo-controlled treatment period Number of participants with PCSA in vital signs during the placebo-controlled treatment period Number of participants with PCSA in 12-lead electrocardiogram (ECG) during the placebo-controlled treatment period

Population ^a	Objectives	Endpoints
PK population	To assess plasma pharmacokinetic (PK) parameters. Concentration at 4 hours post dosing (approximate C _{max} for the parent compound) for lademirsen, its active major metabolite (RG0005), and the sum of lademirsen and RG0005 (SUM) following administration of lademirsen. C _{trough} will be assessed in terms of SUM only.	Plasma concentrations of lademirsen, RG0005, and SUM (lademirsen + RG0005) in C _{max} samples and SUM only in C _{trough} samples during the placebo-controlled treatment period
ADA population	To assess potential formation of anti-drug antibodies (ADAs) following administration of lademirsen.	Incidence and titer of ADAs during the placebo-controlled treatment period Association of AEs with ADAs during the placebo-controlled treatment period
ITT population	To assess the pharmacodynamic effect of lademirsen on changes in kidney injury and function biomarkers.	Change in kidney injury and function biomarkers from baseline at Weeks 24 and 48 during the placebo-controlled treatment period: 
 In blood: blood urea nitrogen (BUN); In urine^b: protein/creatinine ratio, albumin/creatinine ratio, and epidermal growth factor (EGF)/creatinine ratio; In both blood and urine^b: creatinine, Cystatin C, transforming growth factor-β (TGFβ), and neutrophil gelatinase-associated lipocalin (NGAL).
Exploratory		

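### Addendum Table 1 lists only PCSA counts for laboratory, vital-sign and ECG safety, yet is called aligned with protocols that specify observed values and changes from baseline

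*SAP*

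**What the plan says.** **Protocol.** Section 7.1.2 lists three relevant safety endpoints: "Observed values and changes from baseline in clinical laboratory parameters (eg, hematology, chemistry, complement, and urinalysis" (closing bracket omitted), "Observed values and changes from baseline in vital signs" and "Observed changes from baseline in 12-lead ECG". Section 7.2.4 sets the laboratory analysis: "Results and change from baseline for the laboratory parameters will be summarized by treatment group for baseline and each post baseline time point". It then adds shift tables against baseline status and the proportion of subjects with a PCSA. In the protocol the PCSA proportion therefore sits beside the continuous summaries.

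**SAP v2.0.** Table 2 keeps the same endpoints. Section 4.7.3 specifies "The summary statistics (including number, mean, median, Q1, Q3, standard deviation, minimum and maximum) of all laboratory variables", covering values and changes from baseline, by treatment group, at each visit and for the last and worst on-treatment value.

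**SAP addendum, Section 3.** After termination for futility, the final analysis is limited to key endpoints, and Table 1 sets out the modified list, "which is aligned with the endpoints defined in Amended Protocols 11, 12 and 13". In its safety row the laboratory entry is "Number of participants with PCSA in clinical laboratory parameters during the placebo-controlled treatment period". The vital-sign and ECG entries have the same form. None of the three mentions observed values or changes from baseline.

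**Status of the objective.** Safety and tolerability is a primary objective in Protocol 2.1. Footnote c to addendum Table 1 confirms this for Amended Protocols 11 and 12.

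**The concern.** A PCSA count records who crossed a threshold. A change-from-baseline summary records how far the whole group moved. For a small trial of an oligonucleotide, the second is often where a class effect appears first.

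Protocol 1.3.1 names thrombocytopenia as an important identified risk and hepatotoxicity as an important potential risk. Platelets are measured weekly (Protocol 6.2.15), so the data for a by-arm description already exist. If the final report carries only PCSA counts, a moderate platelet, aminotransferase or albumin shift that stays inside the thresholds would not appear in the laboratory tables. A short PCSA table could then be read as showing no signal. The alignment sentence adds to this, because it tells the reader that nothing in the protocol's endpoint list was lost.

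**Working it through.** The documents give no numerical figure to reproduce, so the check is a comparison of texts, followed by the thresholds.

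**1. Is Table 1 aligned?**
- Amended Protocols 11 and 12: the amendment 12 summary of changes lists no change to the safety endpoints, so Section 7.1.2 stands for both. It specifies observed values and/or changes from baseline for all three domains. Table 1 does not.
- Amended Protocol 13 is not among the documents. SAP v2.0, which was written from it, keeps the change-from-baseline endpoints in its Table 2. Table 1 does not match that either.
- What stays continuous in Table 1 is eGFR (efficacy rows) and the kidney and exploratory biomarkers: BUN, creatinine, cystatin C, NGAL, TGF-β, urine protein and albumin ratios, EGF and others. Platelets, liver tests, albumin, hemoglobin and coagulation are not there.

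**2. What do the PCSA criteria in SAP Appendix 8 capture?**
- No change-from-baseline element: platelets (low side <100 Giga/L), ALT and AST (>3, >5, >10 and >20 ULN), alkaline phosphatase (>1.5 ULN), total bilirubin (>1.5 and >2 ULN), albumin (≤25 g/L).
- Some change-from-baseline element: hemoglobin (decrease ≥20 g/L), blood pressure and heart rate (level plus change), weight (≥5% change), PR and QRS (level plus ≥25% increase), QTc (increase of 30-60 ms and of >60 ms).
- No row at all: PT/INR, aPTT and fibrinogen, although SAP 4.7.3.1 lists them as collected. GGT has no row either.

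**3. How coarse is the platelet criterion?**
- <100 Giga/L equals <100 000/microL, the start of Grade 2 in SAP Table 6. Grade 1 (125 000 to 100 000) is not counted.
- The documents give no baseline mean. Assuming 250 Giga/L, a participant must lose more than (250 − 100)/250 = 60% to be counted. Over an assumed 250 ± 55, the range is (195 − 100)/195 = 49% to (305 − 100)/305 = 67%.

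**4. What happened in the sponsor's own multiple-dose study (Protocol 1.1.4.2)?**
- The 220 mg cohort had 8 subjects randomised 3:1, so 8 × 3/4 = 6 on active drug.
- One had a nadir of 92 000/microL. For the others: "The remaining 5 subjects in the 220 mg cohort also experienced a mild reduction in platelet count". Those falls stayed at or above the lower limit of normal. I take that limit to be no lower than 100 000/microL, as Protocol 4.5 implies when it requires recovery from Grade 2 to above it.
- A PCSA count records 1/6. A change summary records a fall in (1 + 5)/6 = 6/6.
- 220/110 = 2, so this cohort received twice the present dose. It illustrates what the count misses and does not predict what will be seen at 110 mg.

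**The case against.** The best defence is that this is an open scope reduction in a terminated study. The addendum gives the reason, the Table 1 title says the list was modified after termination, and PCSA proportions were always part of the protocol's safety analysis. That stands. Nothing is concealed, and a shorter report is legitimate. It does not rescue the alignment sentence, and early termination does not explain dropping double-blind summaries of data already collected.

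Four stronger readings are tempting, and the documents do not support them.

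- A reader might infer that the continuous summaries have been withdrawn. The addendum never expressly withdraws SAP 4.7.2 or 4.7.3, and says the statistical methods are essentially unchanged. The individual platelet and liver plots in 4.7.3, and the graded laboratory summary in 4.7.2 (platelets from 125 000/microL, ALT/AST from 1.25 × ULN), could still be produced. Their status is unclear, and an analyst working from Table 1 would not plan the by-arm change tables.
- A reader might infer that every parameter is reduced to one yes/no cut. ALT and AST have four categories, and hemoglobin, vital-sign, weight and ECG criteria include change from baseline. Adverse event and AESI tables also catch some events below the PCSA level, though not mean shifts.
- A reader might infer a measured loss of power. With about 29 versus 14 participants (43 at 2:1) and 0/14 on placebo, Fisher's test needs 8/29 (p = 0.039; 7/29 gives 0.076). But no version of the plan tests laboratory data, a comparison with mean change needs SDs the documents do not give, and a PCSA counts any on-treatment value, including unscheduled ones, so a one-visit calculation understates the counts.
- A reader might infer that nearly every participant on 110 mg will have a platelet fall. Protocol 1.1.4.2 reports no platelet event at 110 mg, and Protocol 1.1.4.3 reports normal platelet counts in all four Alport patients on 1.5 mg/kg every two weeks.

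**Conclusion.** The point holds in two parts. The alignment statement is wrong as written for the laboratory, vital-sign and ECG endpoints. Restoring the missing summaries is a cheap improvement.

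The consequence is a loss of description and breaks no planned test. It is largest for platelets, liver tests and albumin, whose PCSA criteria ignore change from baseline. It is complete for coagulation, which has no PCSA criterion in Appendix 8 as printed and so no laboratory endpoint under Table 1. It is smaller for hemoglobin, vital signs and ECG.

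The conclusion rests on reading Table 1 together with the restriction to key endpoints as the full list of planned safety outputs. If the sponsor intended SAP 4.7.3 to remain in force, the gap is one of wording, but the addendum does not say so. No assumed mean or SD is needed for the conclusion; the assumed platelet baseline only shows scale.

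**What to change.** In the safety row of addendum Table 1, add descriptive by-arm summaries of observed values and changes from baseline for the double-blind period, next to the PCSA counts. Use the summaries already specified in SAP 4.7.3: by visit, last on-treatment and worst on-treatment. Cover at least platelets, the liver panel, albumin, hemoglobin, coagulation, vital signs and ECG.

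Correct the alignment sentence in addendum Section 3. It should either be true after this change or name the protocol endpoints that are not being analysed and why. State in one line whether SAP 4.7.2 and 4.7.3 still apply to the final analysis.

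No hypothesis tests or confidence intervals are required, since none were planned for these data. No new data or methods are needed. The cost is a wording change and a few more tables in an abbreviated report.

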7.2.6 Other analyses

PK, pharmacodynamic, and exploratory biomarker analyses (see [Section 10.5.2.2](#) for study conduct in China) will be described in the statistical analysis plan finalized before database lock. Measured plasma concentrations (observed PK parameters C_{max} and C_{trough}) for lademirsen (SAR339375), RG0005, and SUM (as applicable) will be summarized using descriptive statistics (eg, mean, standard deviation (SD), median, min-max, and coefficient of variation [%CV]).

The incidence and titer of ADA will be provided by treatment groups. Association between ADA status and safety may be explored.

[REDACTED]

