4.4.3 Supportive secondary endpoint(s)

For the supportive secondary endpoints that are safety, the main analytical approaches are discussed in [Section 4.7](#). For the supportive secondary endpoints that are pharmacokinetic (PK), the main analytical approaches are discussed in [Section 4.8.1](#). For the supportive secondary endpoints that are immunogenicity, the main analytical approaches are discussed in [Section 4.8.2](#). For the supportive secondary endpoints that are biomarkers, the main analytical approaches are described in [Section 4.8.4](#).

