To notice that the AEs must happen within 7 days before or concomitant with the event of direct bilirubin >ULN during the same treatment emergent period. For example, if the event of direct bilirubin >ULN happened on October 1, 2021 00:00AM during the placebo-controlled treatment period, only if the mild Haemorrhage started between September 24, 2021 00:00AM (exclusion) to October 1, 2021 00:00AM (inclusion) during the placebo-controlled treatment period, it will be considered as meeting the criteria of Grade 3 direct bilirubin during the placebo-controlled treatment period.

The **primary focus** of adverse event reporting will be on double blind period in placebo-controlled treatment-emergent events on the safety population unless otherwise specified. Key adverse events will also be summarized for the lademirsen treated population in lademirsen treatment period.

Generalities

If an adverse event date/time of onset (occurrence, worsening, or becoming serious) is incomplete, an imputation algorithm will be used to classify the adverse event as pre-treatment and treatment-emergent periods. The algorithm for imputing date/time of onset will be conservative and will classify an adverse event as treatment emergent unless there is definitive information to determine it is not on treatment emergent periods. Details on classification of adverse events with missing or partial onset dates are provided in [Section 5.3](#).

Adverse event incidence tables will present by SOC, and PT, sorted by internationally agreed order of primary SOC and by decreasing incidence of PTs within each SOC, the number (n) and percentage (%) of participants experiencing an adverse event. Multiple occurrences of the same event in the same participant will be counted only once in the tables within a treatment phase. The denominator for computation of percentages is the defined population (eg, safety population, lademirsen treated population) within each treatment group. Sorting will be based on results of the lademirsen group if the analysis is on DB TE period or the overall group if the analysis is on lademirsen TE period.

Analysis of all treatment-emergent adverse events

- Overview of treatment-emergent adverse events, summarizing number (%) of participants with any
 - Treatment-emergent adverse event,
 - Serious treatment-emergent adverse event,
 - Treatment-emergent adverse event leading to death,
 - Treatment-emergent adverse event leading to dose reduction, and

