4.8.2 Immunogenicity analyses

Data listings will be provided to display results of anti-drug antibody (ADA). If ADA titer value is reported as <xx, the numeric value will be imputed as xx, the minimum required dilution (MRD), and used for summary purposes. Listing will provide results as reported as well as results as imputed.

A patient with at least one anti-drug antibody response at post-baseline visits in the database is considered evaluable.

A patient whose ADA status is positive at baseline is considered to have **pre-existing ADA**.

A patient whose ADA status is positive anytime post-baseline and is negative or missing at baseline is considered to have **treatment-induced ADA**.

A patient whose ADA status is positive at baseline (pre-existing ADA) and the ADA titer level anytime post-baseline is significantly higher than that at baseline is considered to have **treatment-boostered ADA**. A difference in titer values between 2 samples representing greater than or equal to twice the dilution level is considered significant. In other words, the post-baseline titer value divided by the baseline titer value will be greater than or equal to (\geq) 4 to be considered significant. For example, if baseline titer value is 50, the post-baseline titer value has to be ≥ 200 .

For patients with **treatment-induced or treatment-boosted ADA**, the following 3 ADA responses are defined.

Transient ADA response is defined as:

- Treatment-induced or treatment-boosted ADA detected at two or more sampling time points post-baseline, where the first and the last ADA-positive samples (irrespective of any negative samples in between) are separated by a period of less than 16 weeks, and the last sample cannot be treatment induced or treatment-boosted.

Persistent ADA response is defined as:

- Treatment-induced ADA detected at two or more sampling time points post-baseline, where the first and the last ADA-positive sample (irrespective of any negative samples in between) are separated by at least 16 weeks.

Indeterminate ADA response is defined as:

- Only the last sampling time point is positive and all previous samples are negative.

Pre-existing ADA = $100 * (\text{Number of patients with pre-existing ADA at baseline}) / \text{number of evaluable patients}$

ADA Incidence = $100 * (\text{treatment-boosted} + \text{treatment-induced ADA positive patients}) / \text{number of evaluable patients}$

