The following summaries will be provided for placebo-controlled treatment period for safety population:

- Number of ADA evaluable patients
- Number (%) of patients with ADA positive/negative at baseline
- Number (%) of patients that never develop ADA at any time (ie, ADA is always negative post-baseline visits)
- Number (%) of patients with treatment-boosted ADA
- Number (%) of patients with treatment-induced ADA
- Treatment emergent ADA: Number (%) of patients with either treatment-boosted or treatment-induced ADA
- Duration of ADA response: Number (%) of patients with transient/persistent/indeterminate ADA response (each category will be analyzed separately)
- Patients with treatment-induced ADA will be further characterized
 - Peak ADA titer: Median, 25th/75th quantiles, min, max of the ADA titer for peak ADA titer of treatment-induced ADA positive patients
 - Last ADA titer (final assessment): Median and 25th/75th quantiles, min, max of the last ADA titer of treatment induced ADA positive patients

The same summaries will also be provided for **lademirsen treated population** in the **lademirsen treatment period** where baseline will be the last non-missing measure prior to first infusion of lademirsen. The details are discussed in [Section 4.8.5](#).

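### The transient, persistent and indeterminate ADA classes in SAP 4.8.2 are not exhaustive, so the planned ADA duration summary would omit some ADA-positive participants (minor, descriptive)

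*SAP*

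**What the plan says.** After the study was terminated, Table 1 of the SAP addendum kept the ADA endpoints for the ADA population: incidence and titer, and "Association of AEs with ADAs during the placebo-controlled treatment period". The addendum reports no major change in statistical method, and its only new analysis (3.1) concerns eGFR. The ADA rules are therefore those of SAP v2.0. Section 4.4.3 points to them: "For the supportive secondary endpoints that are immunogenicity, the main analytical approaches are discussed in" Section 4.8.2.

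Section 4.8.2 introduces three response classes for patients with treatment-induced or treatment-boosted ADA:

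- **Transient:** "Treatment-induced or treatment-boosted ADA detected at two or more sampling time points post-baseline", with the first and last positives "separated by a period of less than 16 weeks, and the last sample cannot be treatment induced or treatment-boosted".
- **Persistent:** two or more positive time points at least 16 weeks apart. This rule names treatment-induced ADA only.
- **Indeterminate:** "Only the last sampling time point is positive and all previous samples are negative".

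The summaries for the placebo-controlled period then include a duration item: "Number (%) of patients with transient/persistent/indeterminate ADA response (each category will be analyzed separately". The same list reports the number with treatment-emergent ADA, meaning boosted or induced.

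Protocol Table 1 and Section 5.2 schedule double-blind ADA samples at Day 1 and Weeks 1, 2, 3, 4, 12, 24, 36 and 48. Sections 5.4 and 5.5 add samples at early termination (ET) and Follow-up Week 10.

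**The concern.** The classes are offered as a description of all treatment-emergent ADA, so each such participant should fall into one of them. Transient and persistent both need at least two positive samples. Indeterminate accepts one positive, but only at the last sample. A participant with one positive and negatives afterwards is left over. So is one whose positives are confined to the last two 12-weekly visits: they are too close together for persistent, the last sample is positive so transient is ruled out, and two positives rule out indeterminate.

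These patterns are plausible. Protocol 10.5.1.1.3 describes a low incidence of transient responses in healthy volunteers, though after five weekly doses only. The addendum says the study stopped before all Stage 1 participants finished the double-blind period, which makes short, end-loaded patterns more likely.

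What is at stake is the accuracy of one descriptive immunogenicity table. The three counts could fall short of the treatment-emergent ADA count in the same list with nothing to explain the gap, or someone would have to assign the leftover participants after seeing the data.

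**Working it through.** The plan states no figure to reproduce. The check applies the three rules literally to every possible positive/negative pattern.

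**Inputs.** Post-baseline ADA samples at Weeks 1, 2, 3, 4, 12, 24, 36 and 48 (Protocol Table 1, Section 5.2); baseline ADA-negative, so any positive is treatment-induced; rules from SAP 4.8.2.

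**Full schedule.** Patterns with at least one positive: 2^8 − 1 = 255.

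- *Transient* (two or more positives, span under 16 weeks, Week 48 negative). Weeks 1, 2, 3, 4 and 12 all lie within 11 weeks, giving 2^5 − 1 − 5 = 26 subsets of two or more. Adding {12, 24} and {24, 36} gives 28.
- *Indeterminate*: Week 48 only, 1 pattern.
- *No class*: a single positive at Week 1, 2, 3, 4, 12, 24 or 36 (7 patterns), and {36, 48}, where 48 − 36 = 12 weeks and the last sample is positive (1 pattern). Total 8.
- *Persistent*: 255 − 28 − 1 − 8 = 218.

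No pattern meets two rules.

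**Earlier last sample.** The same rules, if the last available sample is Week 36 or Week 24 and no later ET or follow-up sample counts:

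| Last sample | Patterns | Persistent | Transient | Indeterminate | No class |
|---|---|---|---|---|---|
| Week 48 | 255 | 218 | 28 | 1 | 8 |
| Week 36 | 127 | 92 | 27 | 1 | 7 |
| Week 24 | 63 | 30 | 26 | 1 | 6 |

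The unclassified sets include {24, 36} in the second row and {12, 24} in the third.

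**Boosted ADA.** Persistent names induced ADA only. Read literally, the 218 patterns spanning 16 weeks or more then have no class for a boosted participant, so 218 + 8 = 226 of 255 are unclassified (counting a sample as positive when it is at boosted level).

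**What one participant means.** Addendum: Stage 1 only. SAP 1.1: 43 randomized 2:1, so about 43 × 2/3 ≈ 29 on lademirsen. *Assuming* 10% to 50% become ADA-positive, that is about 3 to 15 participants, and each unclassified one is 1/15 = 7% to 1/3 = 33% of the duration summary. This shows the weight of one case, not how often it occurs.

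**After the fix below.** Full schedule: transient 28 + 7 = 35, persistent 218, indeterminate 1 + 1 = 2; 35 + 218 + 2 = 255, none left over.

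**The case against.** Several points against this are fair.

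- *The SAP does not require the classes to sum.* It says each is analyzed separately. True, but 4.8.2 still introduces them as the responses for all induced or boosted ADA, and separate analysis gives an unclassified participant no place.
- *The boosted gap is probably a drafting slip.* The introductory sentence covers boosted ADA, and the pattern needs ADA at baseline, which nothing in the documents suggests is common. This largely stands, so the 226 figure should carry little weight. It does not rescue single positives or end-loaded pairs.
- *ET and follow-up samples could resolve end-loaded pairs.* Partly. If a Follow-up Week 10 sample counted, a participant positive at Weeks 24 and 36 would become transient or persistent according to that sample. But SAP 4.1 ends the placebo-controlled treatment-emergent window 7 days after the last dose for those not continuing, Protocol Table 1 lets the ET sample be skipped if one was taken within 4 weeks, and 4.8.2 does not say which sample is the last. Single positives followed by negatives stay unclassified either way.
- *8 of 255 is about 3%.* It is, but patterns are not equally likely, so the ratio neither shows the problem is rare nor that it is common.

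A reader might also infer a stronger fault: that the AE–ADA association endpoint has no analysis method at all. The documents do not support calling that an error. Protocol 7.2.6 makes exploring the association of ADA status with safety optional. Section 4.8.2 already defines treatment-emergent ADA, which gives the natural yes/no grouping. The layout by arm follows from "The denominator for computation of percentages is the defined population (eg, safety population, lademirsen treated population) within each treatment group" in SAP 4.7.2 and "The incidence and titer of ADA will be provided by treatment groups" in Protocol 7.2.6. ADA and TEAE listings are planned, so onset can be checked participant by participant. The missing table layout and onset rule are omitted detail and form no part of this point.

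**Conclusion.** The class definitions in SAP 4.8.2 are wrong as written, in a minor way. Applied literally, they give no class to a single positive sample that is not the last, to two or more positives less than 16 weeks apart that include the last sample, or to a boosted response spanning 16 weeks or more. The first two do not depend on the drafting-slip question and are the substance of the point. The pattern counts rest on the scheduled visits, complete sampling up to the stated last sample, and a negative baseline. The documents give no basis for estimating how many participants are affected. The consequence is confined to a descriptive ADA duration summary; ADA incidence and titer, the safety tables and the primary eGFR analysis are unaffected.

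**What to change.** Replace the three definitions in SAP 4.8.2, or add them to the addendum before the final database lock:

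- **Transient:** one positive sample that is not the last, or two or more less than 16 weeks apart with the last sample not positive.
- **Persistent:** treatment-induced or treatment-boosted positives at least 16 weeks apart.
- **Indeterminate:** all other treatment-emergent ADA, including positives confined to the final samples.

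Add one sentence stating whether ET and follow-up samples can serve as the last sample for the placebo-controlled period.

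The cost is a few sentences and a small programming change, using data already collected. Indeterminate becomes a residual class, so a footnote should say that it includes responses still positive when sampling ended.
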